APPENDIX 4 WOMEN OF CHILDBEARING POTENTIAL DEFINITIONS AND METHODS OF CONTRACEPTION

Appendix 4 provides general information and definitions related to woman of childbearing potential and methods of contraception that can be applied to most clinical trials. For information specific to this study regarding acceptable contraception requirements for female and male participants, refer to Section 6.1 of the protocol. Only the contraception methods as described in Section 6.1 are acceptable for this study.

DEFINITIONS

Woman of Childbearing Potential (WOCBP)

A woman is considered fertile following menarche and until becoming postmenopausal unless permanently sterile. Permanent sterilization methods include hysterectomy, bilateral salpingectomy, and bilateral oophorectomy.

Women in the following categories are not considered WOCBP:

- Premenarchal
- Premenopausal female with 1 of the following:
 - Documented hysterectomy
 - Documented bilateral salpingectomy
 - Documented bilateral oophorectomy

Note: Documentation can come from the site personnel's review of the participant's medical records, medical examination, or medical history interview.

- Postmenopausal female
 - A postmenopausal state is defined as 12 months of amenorrhea in a woman over age 45 years in the absence of other biological or physiological causes. In addition, females under the age of 55 years must have a serum follicle-stimulating hormone (FSH) level > 40 mIU/mL to confirm menopause.

Note: Females treated with hormone replacement therapy (HRT) are likely to have artificially suppressed FSH levels and may require a washout period in order to obtain a physiologic FSH level. The duration of the washout period is a function of the type of HRT used. Suggested guidelines for the duration of the washout periods for HRT types are presented below. Investigators should use their judgement in checking serum FSH levels.

- 1-week minimum for vaginal hormonal products (rings, creams, gels)
- 4-week minimum for transdermal products
- 8-week minimum for oral products

Other parenteral products may require washout periods as long as 6 months. If the serum FSH level is > 40 mIU/mL at any time during the washout period, the woman can be considered postmenopausal.

End of Relevant Systemic Exposure

End of relevant systemic exposure is the timepoint where the Investigational Medicinal Product (IMP) or any active major metabolites have decreased to a concentration that is no longer considered to be relevant for human teratogenicity or fetotoxicity. This should be evaluated in context of safety margins from the no-observed-adverse-effect level or the time required for 5 half-lives of the IMP to pass.

METHODS OF CONTRACEPTION

Local laws and regulations may require use of alternative and/or additional contraception methods.

Highly Effective Contraceptive Methods That Are User Dependent

Failure rate of < 1% per year when used consistently and correctly. ^a

- Combined (estrogen- and progestogen-containing) hormonal contraception associated with inhibition of ovulation and/or implantation. (This method of contraception can only be used by WOCBP participants in studies where hormonal contraception is permitted by the study protocol.)^b
 - Oral (birth control pills)
 - Intravaginal (rings)
 - Transdermal
- Combined (estrogen-and progestogen-containing) hormonal contraception must begin at least 30 days prior to initiation of study therapy.
- Progestogen-only hormonal contraception associated with inhibition of ovulation. (This method of contraception can only be used by WOCBP participants in studies where hormonal contraception is permitted by the study protocol.)^b
 - Oral
 - Injectable
- Progestogen-only hormonal contraception must begin at least 30 days prior to initiation of study therapy.

Highly Effective Methods That Are User Independent

- Implantable progestogen-only hormonal contraception associated with inhibition of ovulation and/or implantation. (This method of contraception can only be used by WOCBP participants in studies where hormonal contraception is permitted by the study protocol.)^b
- Intrauterine device.
- Intrauterine hormone-releasing system (IUS). (This method of contraception can only be used by WOCBP participants in studies where hormonal contraception is permitted by the study protocol.)^{b,c}

• Bilateral tubal occlusion.

Vasectomized partner

Having a vasectomized partner is a highly effective contraception method provided that the partner is the sole male sexual partner of the WOCBP and the absence of sperm has been confirmed. If not, an additional highly effective method of contraception should be used.

A vasectomy is a highly effective contraception method provided that the participant is the sole male sexual partner of the WOCBP and the absence of sperm has been confirmed. If not, an additional highly effective method of contraception should be used.

• Sexual abstinence.

Sexual abstinence is considered a highly effective method only if defined as refraining from heterosexual intercourse during the entire period of risk associated with the study treatment. The reliability of sexual abstinence needs to be evaluated in relation to the duration of the study and the preferred and usual lifestyle of the participant.

- Continuous abstinence must begin at least 30 days prior to initiation of study therapy.
- It is not necessary to use any other method of contraception when complete abstinence is elected.
- WOCBP participants who choose complete abstinence must continue to have pregnancy tests, as specified in Section 2.
- Acceptable alternate methods of highly effective contraception must be discussed in the event that the WOCBP participant chooses to forego complete abstinence.
- Periodic abstinence (including, but not limited to, calendar, symptothermal, postovulation methods), withdrawal (coitus interruptus), spermicides only, and lactational amenorrhea method (LAM) are not acceptable methods of contraception for this study.

NOTES:

- ^a Typical use failure rates may differ from failure rates when contraceptive methods are used consistently and correctly. Use should be consistent with local regulations regarding the use of contraceptive methods for participants in clinical studies.
- Hormonal contraception may be susceptible to interaction with the study treatment, which may reduce the efficacy of the contraceptive method. Hormonal contraception is permissible only when there is sufficient evidence that the IMP and other investigational products will not alter hormonal exposures such that contraception would be ineffective or result in increased exposures that could be potentially hazardous. In this case, alternative methods of contraception should be utilized. For information specific to this study regarding permissibility of hormonal contraception, refer to Sections 6.1 INCLUSION CRITERIA and 7.7.2 PROHIBITED
- IUSs are acceptable methods of contraception in the absence of definitive drug interaction studies when hormone exposures from intrauterine devices do not alter contraception effectiveness. For information specific to this study regarding permissibility of hormonal contraception, refer to Sections 6.1 INCLUSION CRITERIA and 7.7.2 PROHIBITED of the protocol.

Less Than Highly Effective Contraceptive Methods That Are User Dependent

Failure rate of > 1% per year when used consistently and correctly.

- Male or female condom with or without spermicide. Male and female condoms cannot be used simultaneously.
- Diaphragm with spermicide.
- Cervical cap with spermicide.
- Vaginal sponge with spermicide.
- Progestogen-only oral hormonal contraception, where inhibition of ovulation is not the primary mechanism of action. (This method of contraception cannot be used by WOCBP participants in studies where hormonal contraception is prohibited.)

Unacceptable Methods of Contraception

- Periodic abstinence (calendar, symptothermal, postovulation methods).
- Withdrawal (coitus interruptus).
- Spermicide only.
- LAM.

COLLECTION OF PREGNANCY INFORMATION

Guidance for collection of pregnancy information and outcome of pregnancy on the Pregnancy Surveillance Form is provided in Section 9.2.6 and Appendix 3, the appendix for Adverse Events and Serious Adverse Events: Definitions and Procedures for Recording, Evaluating, Follow-up, and Reporting.

APPENDIX 5 CLASSIFICATION CRITERIA FOR PSORIATIC ARTHRITIS (CASPAR) CRITERIA

CASPAR CRITERIA (Specificity 0.987, Sensitivity 0.914)			
Inflammatory articular disease (joint, spine, or entheseal) With 3 or more points from the following			
2. Personal history of psoriasis (if current psoriasis not present)	A history of psoriasis that may be obtained from patient, family doctor, dermatologist, or rheumatologist		
Family history of psoriasis (if personal history of psoriasis or current psoriasis not present)	A history of psoriasis in a first or second degree relative according to patient report		
4. Psoriatic nail dystrophy	Typical psoriatic nail dystrophy including onycholysis, pitting, and hyperkeratosis observed on current physical examination		
5. A negative test for rheumatoid factor	By any method except latex but preferably by ELISA or nephlemetry, according to the local laboratory reference range		
6. Current dactylitis	Swelling of an entire digit		
7. History of dactylitis (if current dactylitis is not present)	A history of dactylitis recorded by a rheumatologist		
8. Radiological evidence of juxta-articular new bone formation	Ill-defined ossification near joint margins (but excluding osteophyte formation) on plain X-rays of hand or foot		

Reference:

[figure not shown]
APPENDIX 6 SUBJECT ASSESSMENT OF DISEASE ACTIVITY (PSORIATIC ARTHRITIS) VISUAL ASSESSMENT SCALE

In all the ways in which your psoriatic arthritis as a whole, affects you, how would you rate the way you felt over the past week?

[figure not shown]

[figure not shown]
APPENDIX 7 SUBJECT ASSESSMENT OF PAIN SCALE (PSORIATIC ARTHRITIS)

How much pain have you had because of your psoriatic arthritis over the past week? Place a mark on the line below to indicate how severe your pain has been:

[figure not shown]

APPENDIX 8 AMERICAN COLLEGE OF RHEUMATOLOGY SUBJECT ASSESSMENT OF PHYSICAL FUNCTION SCALE: HEALTH ASSESSMENT QUESTIONNAIRE (HAQ)

[figure not shown]

[figure not shown]

[figure not shown]

[figure not shown]

[figure not shown]

[figure not shown]

[figure not shown]

[figure not shown]

[figure not shown]

[figure not shown]

[figure not shown]

[figure not shown]

[figure not shown]
APPENDIX 10 FUNCTIONAL ASSESSMENT OF CHRONIC ILLNESS THERAPY FATIGUE

[figure not shown]

[figure not shown]

[figure not shown]
APPENDIX 12 DERMATOLOGY LIFE QUALITY INDEX (DLQI)

[figure not shown]
APPENDIX 13 EURO QUALITY OF LIFE FIVE DIMENSIONS QUESTIONNAIRE: 5-LEVEL VERSION (EQ-5D-5L)

[figure not shown]

[figure not shown]

APPENDIX 15 WORK PRODUCTIVITY AND ACTIVITY IMPAIRMENT QUESTIONNAIRE: PSORIATIC ARTHRITIS (WPAI:PSA)

[figure not shown]

[figure not shown]
APPENDIX 16 THE BATH ANKYLOSING SPONDYLITIS DISEASE ACTIVITY INDEX (BASDAI)

APPENDIX 17 PHYSICIAN'S GLOBAL ASSESSMENT OF PSORIATIC ARTHRITIS

How would you rate global skin and musculoskeletal disease in this patient?

APPENDIX 19 STATIC PHYSICIAN'S GLOBAL ASSESSMENT OF PSORIASIS (SPGA)

The static Physician's Global Assessment (sPGA) is used to determine the participant's psoriasis lesions overall at a given time point. Overall lesions will be graded for erythema, induration, and scaling based on the scales below. The average of the 3 scales, which is rounded to the nearest whole number, is the final sPGA score.

Characteristics	Score	Rating Score
Erythema (E) (averaged over the whole body)		 0 = No evidence of erythema, but post inflammatory hyper/hypopigmentation changes may be present 1 = Faint erythema 2 = Light red coloration 3 = Moderate red coloration 4 = Bright red coloration
Induration (I) (averaged over the whole body)		 0 = No evidence of plaque elevation 1 = Minimal plaque elevation, barely palpable, = 0.25 mm 2 = Mild plaque elevation, slight but definite elevation, indistinct edge, = 0.5 mm 3 = Moderate plaque elevation, elevated with distinct edges, = 0.75 mm 4 = Severe plaque elevation, hard/sharp borders, ≥1 mm
Scaling (S) (averaged over the whole body)		0 = No evidence of scaling 1 = Minimal; occasional fine scaling 2 = Mild; fine scale dominates 3 = Moderate; coarse scale predominates 4 = Severe; thick scale predominates

E + I + S = /3 = (Total Average)

sPGA based upon above total average

- 0 = Clear, except for residual discoloration
- 1 = Almost clear -majority of lesions have individual scores for E + I + S / 3 that averages 1
- 2 = Mild -majority of lesions have individual scores for E + I + S / 3 that averages 2
- 3 = Moderate -majority of lesions have individual scores for E + I + S / 3 that averages 3
- 4 = Severe -majority of lesions have individual scores for E + I + S / 3 that averages 4

Note: Scores should be rounded to the nearest whole number. If total \le 1.49, score = 1; if total \ge 1.50, score = 2.

APPENDIX 20 PHYSICIAN'S GLOBAL ASSESSMENT OF FINGERNAILS (PGA-F SCORING)

Instructions:

- Subject's fingernails need to be globally assessed separately for nail bed signs and nail matrix signs of disease, following the criteria specified below. A global score between '0' (clear) and '4' (severe) should be separately assigned for nail bed involvement and nail matrix involvement. A subject's overall global score is the worse of the nail bed score and nail matrix score. For example, if a subject has a nail bed score of '2' and a nail matrix score of '4,' this subject's overall score is '4.'
- If a subject has signs of nail bed (or nail matrix) disease intermediate
 between two grades, then the subject's nail bed (or nail matrix score)
 should be assigned the higher
 of the two grades. For example, if a subject's nail bed hyperkeratosis is
 considered to be worse than 'mild' but less than 'moderate', and all other
 nail bed signs are mild or less, the subject's nail bed score should be
 considered 'moderate.'
- Please record your patient's degree of Nail Bed Signs by selecting the appropriate descriptor in the Nail Bed Signs column below.
 -AND-

Please record your patient's degree of Nail Matrix Signs by selecting the appropriate descriptor in the Nail Matrix Signs column below.

	Nail Bed Signs	Nail Matrix Signs ^{a,b}
Clear (0)	Onycholysis: consistent with a normal nail AND Hyperkeratosis: none, AND Splinter hemorrhages: consistent with non- psoriatic splinter hemorrhages, AND No evidence of nail bed erythema	No non-psoriatic nail plate irregularities including pitting, crumbling, Beau's lines, senile onychorrhexis, and non-psoriatic leukonychia.
Minimal (1)	Onycholysis: < 10% involvement on all nails, OR Hyperkeratosis: present with barely detectable elevation of nail plate, OR Faint nail bed erythema, AND Splinter hemorrhages: consistent with non- psoriatic splinter hemorrhages	No more than 5 pits or psoriatic leukonychia on any nail, AND No crumbling
Mild (2)	Onycholysis: > 10% involvement on five or more nails, OR Hyperkeratosis: present with mild elevation of nail plate, OR Splinter hemorrhages: present on four or less nails, OR Mild nail bed erythema	Five or more nails with mild pitting (e.g., > 10 pits) or psoriatic leukonychia, AND No crumbling

	Nail Bed Signs	Nail Matrix Signs ^{a,b}
Moderate (3)	Onycholysis: > 30% involvement on at least one nail, OR Hyperkeratosis: present with at least moderate elevation of nail plate, OR Splinter hemorrhage: scattered and present on five or more nails, OR Moderate nail bed erythema	Five or more nails with moderate pitting (e.g., > 25 pits/nail) or psoriatic leukonychia, AND ≤ 25% crumbling on all nails
Severe (4)	Onycholysis: > 50% involvement on at least one nail, OR Hyperkeratosis: present with severe elevation of nail plate, OR Splinter hemorrhages: numerous and present on five or more nails, OR Severe nail bed erythema	Five or more nails with severe pitting (e.g., > 50 pits/nail) or psoriatic leukonychia, OR > 25% crumbling on any nail

Evidence of psoriatic leukonychia should be counted toward the presence of pits. Confluent pits causing marked indentation of the nail plate should be considered crumbling.

Extent of crumbling defined by % of nail plate surface area missing or abnormal due to crumbling.

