To assess the efficacy of deucravacitinib (6 mg QD) to placebo as assessed by DAPSA score up to Week 16	 Change from baseline in DAPSA score Proportion of participants with achievement of DAPSA Low Disease Activity response Proportion of participants with 		
	achievement of DAPSA disease remission		
To assess the efficacy of deucravacitinib (6 mg QD) to placebo as measured by PGA-F up to Week 16	Proportion of participants meeting achievement of PGA-F of $0/1$ in participants with a baseline PGA-F score of ≥ 3		
To assess the efficacy of deucravacitinib (6 mg QD) to placebo up to Week 16 in	Change from baseline in DAS28-CRP score		
DAS28-CRP	Proportion of participants with achievement of a DAS28-CRP Low Disease Activity response		
	Proportion of participants with achievement of a DAS28-CRP disease remission		

Table 4-1: Objectives and Endpoints

Objective	Endpoint
To assess the efficacy of deucravacitinib (6 mg QD) to placebo as measured by the PASDAS up to Week 16	Change from baseline in PASDAS
To assess the efficacy of deucravacitinib (6 mg QD) in mCPDAI score up to Week 16	Change from baseline in mCPDAI score
To assess the efficacy of deucravacitinib (6 mg QD) to placebo as measured by the PsARC up to Week 16	Proportion of participants achieving PsARC, where participants must achieve improvement in 2 of 4 measures, 1 of which must be joint pain or swelling, without worsening in any measure
To assess the efficacy of deucravacitinib (6 mg QD) to placebo as measured by the BASDAI score up to Week 16	Proportion of participants meeting achievement of improvement from baseline in BASDAI score among participants with spondylitis in addition to peripheral joint involvement as their presentation of PsA
To assess inhibition of structural damage up to Week 16	 Proportion of participants meeting achievement of total PsA-modified SvdH score of ≤ 0, ≤ 0.5, and ≤ SDC at Week 16 Proportion of participants meeting achievement of PsA-modified SvdH erosion score change of ≤ 0, ≤ 0.5, and ≤ SDC at Week 16 Proportion of participants meeting achievement of PsA-modified SvdH JSN score change of ≤ 0, ≤ 0.5, and ≤ SDC at Week 16 Change in PsA-modified SvdH erosion score from baseline at Week 16 Change in PsA-modified SvdH JSN score at Week 16

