9.1.16 Physician Global Assessment-Fingernails

In this assessment, the overall condition of the fingernails is rated on a 5-point scale:

0 = clear, 1 = minimal, 2 = mild, 3 = moderate, and 4 = severe

The PGA-F will be performed only in participants with psoriatic fingernail involvement to assess severity and subsequent improvement. An example is provided in Appendix 20. The PGA-F should be performed by an appropriately trained assessor experienced in the assessment of PsO patients.

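### Appendix 20 words the nail-matrix Clear (0) grade of the PGA-F the wrong way round: it bars non-psoriatic nail changes and does not bar psoriatic ones

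*Combined protocol and SAP*

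**What the plan says.** Appendix 20 has raters grade nail-bed and nail-matrix disease separately, each from 0 to 4. The overall PGA-F is the worse of the two, and a sign of disease that falls between two grades takes the higher one.

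- Clear (0), nail matrix: "No non-psoriatic nail plate irregularities including pitting, crumbling". The list then goes on to Beau's lines, age-related ridging (onychorrhexis) and leukonychia that is not psoriatic.
- Clear (0), nail bed, same row: "Splinter hemorrhages: consistent with non- psoriatic splinter hemorrhages, AND No evidence of nail bed erythema".
- Minimal (1), nail matrix: "No more than 5 pits or psoriatic leukonychia on any nail, AND No crumbling".
- Mild (2), nail matrix: "Five or more nails with mild pitting (e.g., > 10 pits) or psoriatic leukonychia, AND No crumbling".

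Moderate (3) and Severe (4) set higher pitting thresholds (examples above 25 and above 50 pits per nail, on five or more nails). Moderate also needs crumbling of 25% or less on all nails; crumbling above 25% on any nail is enough for Severe.

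Section 9.1.16 gives the purpose: "The PGA-F will be performed only in participants with psoriatic fingernail involvement to assess severity and subsequent improvement". Table 4-1 lists the proportion reaching PGA-F 0 or 1, "in participants with a baseline PGA-F score of" 3 or more, among the additional secondary endpoints up to Week 16.

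**The concern.** A Clear grade on a psoriasis scale should mean that no psoriatic sign is present. The nail-matrix cell sets a different condition. It asks for the absence of changes that are, by its own wording, not psoriasis, and it is silent on those that are. Two errors are then possible. A participant whose nail psoriasis has gone can be refused a 0 because of ridging that comes with age. A nail with psoriatic pits and no other change can satisfy the Clear cell.

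At stake is consistency of scoring. Raters who follow the printed cell and raters who follow its evident intent will grade the same nail differently, on a scale that feeds a secondary endpoint and also defines, through the baseline score, who is analysed for it.

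**Working it through.** The plan gives no figure to reproduce here, so the check sets the cells side by side and then runs example findings through the nail-matrix column.

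**Is the cell inverted?** Four places in the documents point the same way.

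1. The nail-bed cell in the same row accepts splinter hemorrhages of a non-psoriatic kind at grade 0. The matrix cell rejects non-psoriatic change at grade 0.
2. The Appendix 20 instructions ask for signs of disease to be graded. Age-related ridging and non-psoriatic leukonychia are not signs of the disease under study.
3. Grades 1 to 4 and the note under the table count only psoriatic leukonychia, so the author separated the two kinds of change.
4. Section 9.1.16 says that the scale follows psoriatic fingernail involvement.

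Nothing visible supports making non-psoriatic change the test for Clear.

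**What does the literal text do to scores?** Inputs are the five nail-matrix cells as printed. For this test, pits and crumbling in grades 1 to 4 are counted whatever their cause, because those cells do not limit them to psoriasis. The last column assumes a nail-bed score of 0 or 1. In every row except the last, nail psoriasis has cleared.

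| Nail-matrix finding | Grades whose cell is met | PGA-F 0/1 |
|---|---|---|
| Normal nails | 0 and 1 | Response |
| Beau's lines, ridging or non-psoriatic leukonychia | 1 | Response |
| 3 non-psoriatic pits on each of 2 nails | 1 | Response |
| 8 non-psoriatic pits on each of 2 nails | none | Undefined |
| Non-psoriatic crumbling, 10% | none | Undefined |
| 15 non-psoriatic pits on each of 5 nails | 2 | Non-response |
| Non-psoriatic crumbling, 30% | 4 | Non-response |
| 60 psoriatic pits on each of 6 nails, no other change | 0, 2, 3 and 4 | Depends on grade chosen |

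The two undefined rows become non-response if a rater stretches the rule for intermediate findings to cover them, but that rule is written for signs of disease. For the last row, the visible instructions do not say what to do when a nail fits several grades of one column.

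**What changes if the cell is corrected?** If Clear means no psoriatic matrix signs and tolerates non-psoriatic ones, the first seven findings meet grade 0. The second and third move from 1 to 0 with response unchanged. The last finding no longer meets Clear and falls in the disease grades, with Severe the highest met. Under the corrected cell, 15 non-psoriatic pits or 30% crumbling would still also match grades 2 and 4 for a rater who ignored the instruction to grade disease, so the correction should be read together with that instruction.

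**The case against.** The strongest reply is that the practical effect is small. Response is 0 or 1, so three of the five signs named in the cell cannot by themselves alter it, and neither can up to 5 pits on a nail. The pitting and crumbling cases need a rater to count non-psoriatic lesions despite the instruction to grade disease, and Section 9.1.16 calls for a trained assessor experienced in psoriasis. PGA-F is not among the key secondary endpoints, and no visible endpoint uses PGA-F 0 alone. The wording is the same in both blinded arms. All of this stands.

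There are also limits on what can be seen. Amendment 02 lists Appendix 20 among its changes without a visible description, some endpoint rows are not shown, and rater training material is not part of the documents. Words lost when the text was extracted cannot be fully excluded, although the sentence reads as complete.

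What the reply does not do is defend the cell. It relies on raters overriding the printed anchor, and it does not address psoriatic pitting that meets Clear.

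A reader might infer three stronger things. The first is that cleared participants will in general be counted as non-responders. The table above shows that this is so only for heavier non-psoriatic pitting or crumbling, scored literally. The second is that the endpoint loses a stated amount of power. The documents give no frequency of non-psoriatic nail change, no size for the nail subset and no assumed PGA-F response rates, and PGA-F is not a row in Table 10.3.1-1, so any such figure would be invented. The third is that the error favours one arm. Identical wording under blinding gives no reason to expect that.

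**Conclusion.** The nail-matrix Clear (0) descriptor is wrong as written, and it contradicts both the nail-bed cell beside it and the instruction to grade disease. Its main effect is to blur 0 and 1. PGA-F 0/1 response changes only with more than 5 non-psoriatic pits on a nail, with non-psoriatic crumbling, or with psoriatic pitting graded Clear, and each of these requires the printed text to be applied literally. The same literal scoring of pits or crumbling could raise a baseline score to 3 or more, but Section 9.1.16 limits the scale to participants with psoriatic nail involvement. The expected result is rater noise in both arms. Its size cannot be estimated from the documents. The primary and key secondary endpoints are not affected. The conclusion assumes that the printed sentence is complete.

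**What to change.** Reconcile the Clear (0) nail-matrix cell with the nail-bed column and with the instruction to grade signs of disease. Clear should mean that there are no psoriatic nail-matrix signs, and non-psoriatic irregularities should not prevent a 0. Check the new wording against the source instrument, send the corrected page to raters, and record which PGA-F scores were taken before the correction.

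The cost is one table cell and one rater communication, with no new assessments. The small downside is that scores already taken cannot be re-read, which is why the date of the change should be kept with the data.
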